**Preliminary Data:** The pilot study (N=65) for ASAP/BRITE was conducted by these two sites. Adolescents (ages 12 to 17) who were hospitalized with recent ideation with plan or intent and/or a recent suicide attempt were randomized to receive ASAP + BRITE + TAU or TAU alone. Participants were balanced both within and across sites on age (12-15 vs. 16-17.11), gender, and past attempt. Suicidal ideation (Suicidal Ideation Questionnaire – Junior) and behavior (Columbia Suicide Severity Rating Scale, C-SSRS) were assessed at weeks 4, 12, and 24 by independent evaluators. The intervention was accepted by a high proportion of those patients who were eligible (65%). Those in the ASAP group, compared to those in TAU had fewer attempts over time (13.3% vs. 31.0%, p=.10, Hedge's g = .44), and a longer time from baseline to attempt than TAU (adjusted HR=0.22, 95% CI: 0.05, 0.85, z=-2.19, p = 0.03). Prior attempts moderated treatment, such that those who had a prior attempt (2/3 of the sample) and received ASAP had a much lower hazard of time to reattempt (HR=0.12, 95% CI: 0.01, 0.94, z=-2.02, p=0.04). There was a non-significant trend for those assigned to ASAP to be less likely to be re-hospitalized (10.0% vs. 24.1%,  $\chi^2_1=2.09$ , p=0.15, g=-0.38). Also, ASAP + BRITE + TAU, in moderator analyses, reduced suicidal ideation in those with lower reasons for living and more dysfunction emotion regulation. Participants whose families participated in the intervention showed slightly lower rates of attempt during the study (11.1% vs. 14.3%, p>0.99), lower

hazard of attempt (HR=0.72, 95%CI: 0.07, 6.88,  $p=0.77$ ) and more decreasing SIQ scores over time ( $\beta=-0.61$ , 95%CI: -1.12, -0.11,  $p=0.02$ ). Of those participants who received the phone app, 72.7% viewed the app, and of these 75% added content with an average use of almost 30 times. More frequent response to prompts from the app for mood check-in, was associated with improvement on reasons for living ( $p=0.37$ ,  $p=0.08$ ) and declines in suicidal ideation ( $\rho=-0.37$ ) over the 24- week follow-up period (see figure below).

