##### Treatment Intervention (ASAP)

[figure not shown]
The ASAP intervention model is designed to increase protection against adolescents acting on their suicidal urges and attempting suicide. We use a motivational interviewing (MI) framework for the intervention. The four modules are as follows: 1. treatment overview and psychoeducation about suicidal behavior, chain analysis, reasons for living, and safety planning; 2. distress tolerance techniques 3. savoring techniques for the maintenance of positive mood by reminiscing on recent positive events are taught, along with the practice of “switching” strategies designed to build resilience to stressors that may destabilize mood (29); and 4. review of the ASAP skills and safety plan with the teens and their family members (as available). Quality assurance ratings will be obtained on a random sample of 20% of ASAP sessions. Up to two bridging calls (2) to the participant will be made at 1 and 2 weeks after discharge to review use of safety plan and ASAP components, and assess adherence to follow-up care.

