## BRITE ALONE

The BRITE only condition will consist of a one session (1 hour) visit with a study therapist who will conduct safety planning, specifically identifying the triggers of the suicide attempt/event using a chain analysis approach. In addition, the therapist will assist the patient in recognizing existing coping skills. The BRITE ALONE intervention will also include up to two bridging calls (2) to the participant that will be made at 1 and 2 weeks after discharge to review use of BRITE, and assess adherence to follow-up care.

The BRITE app intervention will include using an emotional thermometer to identify markers of "point of no return" and ask the participant to identify strategies that could be used to de-escalate (avoid triggers, distraction, calling family support/ professionals, reasons for living, deep breathing, mindfulness, emergency contacts). Information from the chain analysis, coping skills assessment, and emotional thermometer discussion will assist the therapist and patient in populating the BRITE app. Finally the therapist and patient will identify barriers that might interfere with the patient's ability to use their plan. The Safety Plan will include: (1) a family component that includes the following: asking the patient to explain the safety plan to the parents, getting parental feedback, asking both parents and patient what might get in the way of implementing the plan, considering either ways to overcome those barriers or revising the plan, and (2) removing/securing lethal agents. The patient should be referred for emergency evaluation if they clearly express suicidal intent and are unwilling to commit to the safety plan. Clinical conditions that would impede ability to adhere to a safety plan include: psychosis, bipolar disorder (rapid cycling or mixed state), alcohol and drug abuse, and a traumatic brain injury.

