### ASAP + BRITE + TAU:

In this treatment condition, we will combine treatment as usual with ASAP and the phone app as we did in the pilot study (N = 65). The study therapist will provide the ASAP components that are described above, and assist the patient in populating the app with the ASAP strategies (safety plan, reasons for living, distress tolerance, savoring, supportive and professional contacts). The family will be included in the treatment to review ASAP skills and the phone app.

Treatment as Usual. The focus of inpatient care across sites is on diagnosis, safety assessment, development of a safety plan, stabilization, initiation or adjustment of pharmacotherapy, psychoeducation for patients and families, and disposition. Clinical referrals for outpatient treatment will be provided prior to discharge. Unit therapists develop a safety plan with the patient and family, although there is no standard protocol for doing so. For participants in the ASAP only group, BRITE only group, and ASAP + BRITE + TAU, therapists will expand on the inpatient safety plan to include emotion regulation and distress tolerance strategies.

The ASAP + TAU, BRITE + TAU, and ASAP + BRITE + TAU treatment will be front-loaded, meaning that each will either precede discharge or commence within one week of discharge to recommended outpatient psychiatric treatment. Study therapists will be trained to deliver all three active treatment arms. TAU will be provided by inpatient staff. Researchers will also send a letter regarding participation in the study to the subject's outpatient therapist.

*Randomization.* Participants will be randomized centrally at WPIC by a web-based computer program that has been used successfully in other studies ([name] et al., 2008; Garber et al., 2009). The study coordinator at each site will complete a Randomization Request form on the secure website. Once the form is completed, a database trigger will run the randomization program to determine the group assignment. The program will automatically generate and send an email to the study coordinator and the data coordinating center to notify them of the assignment. Participants will be balanced both within and across sites on age (12-15 vs. 16-17.11), and past attempt vs. high ideation. To increase the gender and ethnic diversity in the overall sample, we will oversample males and individuals from minority groups to include 25% males and 35% minority groups.

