### Assessments (see Table 1):

Follow-up assessments using independent evaluators blind to treatment condition will be conducted at Weeks 4, 12, and 24. TAU or standard care on the inpatient unit includes diagnosis, safety assessment and stabilization, initiation or adjustment of pharmacotherapy, psychoeducation of patients and families, and disposition. It is standard care for the inpatient units to provide clinical referrals for outpatient treatment and typically a follow-up appointment occurs about 1 week after discharge. We will also directly measure TAU services post hospitalization using a service use assessment instrument (CASA – see measures section).

Demographics, including gender identity and sexual orientation (as per requirements by AFSP research grants) will be collected at baseline. We will compare the four treatment conditions with respect to three main sets of outcomes: (1) efficacy at reducing suicidal ideation, and increasing time to suicidal attempt and (2) moderators and mediators related to suicidal outcomes, (3) cost effectiveness of each intervention alone and combined compared to TAU.

To shorten the diagnostic assessment, dimensional measures of psychopathology will be obtained from the parent, using the Strengths and Difficulties Questionnaire (SDQ; Goodman, 1997) and the corresponding Youth Self Report (YSR) from the participant (Achenbach, 1991) at intake. Diagnostic assessment will include dimensional measures of anxiety (the Screen for Anxiety Related Disorders [SCARED, 5 item scale]) (Birmaher et al., 1999), depression (Patient Health Questionnaire [PHQ-9]) (Johnson, Harris, Spitzer, & Williams, 2002; Richardson et al., 2010), alcohol and drug use (CRAFFT-self report substance use screening tool) (Knight et al., 1999), and sleep disturbance (Pittsburgh Sleep Quality Index [PSQ]; Buysse, Reynolds, Monk, Berman, & Kupfer, 1989). These measures will be obtained at each follow up, since these are often targets of group and individual treatment and because these may be potential moderators of use of the safety plan and of suicidal ideation change.

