#### Primary aims.

Hypothesis 1. Both ASAP and BRITE will be superior to TAU alone, and ASAP + BRITE + TAU will be superior to BRITE or ASAP alone.

Our main analysis will be the use of two-way ANOVA with an interaction term. We will use the assessments from the instruments listed in Table 1 to study the three main outcomes. For SI severity, we will use a linear model; for NSSI and suicide attempts, we will use a Poisson model; and for the time to attempt, we will use the Cox model. We will include as covariates the following: site, the three covariates we balanced on in our randomization, and any covariates we find in our preliminary analyses to be associated with the outcome; we will consider mixed effects models if they provide a better fit. We do not expect a strong interaction term; if so, our inferences will be based on the main effects. As additional analyses, we will use post-hoc tests for the four main comparisons: the combination vs. each component, and each component vs. TAU.

H2: The effects of ASAP and BRITE will be mediated by increases in reasons for living, decreases in dysfunctional emotional regulation, increases in functional emotional regulation, and decreases in implicit associations with death, and will be moderated by previous history of an attempt, and family engagement in treatment. In addition, the impact of BRITE will be proportional to the frequency of use.

For moderator and mediator analyses, we use the standard approach of Baron and Kenney (1986) and later explicated by Kraemer and colleagues (2002) and Kraemer (2008) for moderators. The search for moderators is typically an exploratory analysis because it involves the testing of interaction terms, for which power is usually limited. Thus, we will use the recent optimal weighted moderator profiles developed by Wallace, Frank, and Kraemer (2013) that combine potential (weaker) moderators. For mediator analyses, we will follow the approach of Preacher and Hayes (2008) for handling multiple mediators. In particular, we will begin by including the candidate mediators listed above in a single model and test their significance using both standard errors using the Gaussian model or the bootstrap if the Gaussian model is not a good fit.

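### H2 names family engagement in treatment as a moderator, but engagement arises after randomisation, so an interaction with it can reflect who engages in each arm and not effect modification

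*Combined protocol and SAP*

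**What the plan says.** H2 appears in the Specific Aims and in the Primary aims part of the statistical analysis. It names exactly two moderators: the effects "will be moderated by previous history of an attempt, and family engagement in treatment". Prior attempt is one of the factors on which randomisation is balanced.

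Family contact is described as part of what the study arms deliver:

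- ASAP, module 4: "review of the ASAP skills and safety plan with the teens and their family members (as available".
- BRITE alone: the safety plan has "a family component that includes the following: asking the patient to explain the safety plan to the parents".
- Combined arm: "The family will be included in the treatment to review ASAP skills and the phone app".
- TAU: inpatient staff provide it. They teach families and draw up a safety plan with them, but without a set procedure.

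Table 1 has no measure of family engagement. FACES-IV, at baseline only, measures family climate and is already listed among the possible moderators under Outcome measures.

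The Assessments section says of the anxiety, depression, substance-use and sleep scales: "These measures will be obtained at each follow up, since these are often targets of group and individual treatment", and also "because these may be potential moderators of use of the safety plan and of suicidal ideation change".

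The H2 analysis text calls the search for moderators typically exploratory and plans to merge weaker moderators into one weighted profile. Nowhere does the plan limit moderators to baseline values.

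**The concern.** A moderator analysis keeps the protection of randomisation only if the moderator could not have been affected by assignment. Within a stratum fixed before assignment, the arms are still randomised groups. Within a stratum defined by engagement afterwards, they need not be: the families who attend an ASAP session and those counted as engaged under TAU may differ in prognosis. The arm contrast inside each stratum then mixes treatment with selection.

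At stake is half of H2's moderator claim. A significant interaction could be read as evidence that the programme works when families take part, and could steer dissemination, when it only shows which families took part. Because moderators are to be combined, the same variable could also enter the composite profile.

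**Working it through.** **1. The plan's own figure.** The plan gives no number for moderation; for H2, the Power Analyses section speaks of detectable effects only in words. The nearest figure that can be computed is d of about 0.55 for two cells of 51: (1.960 + 0.842) × √(2/51) = 0.555. Power at d = 0.55 is 79.3% (normal) or 78.5% (t). It reproduces. The total of 204 is used below as the plan states it.

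**2. The pilot precedent.** The Preliminary Data report: "Participants whose families participated in the intervention showed slightly lower rates of attempt during the study (11.1% vs. 14.3%, p>0.99". Attempt rates by arm were 13.3% and 31.0%, which fit 4/30 and 9/29. The rehospitalisation rates of 10.0% and 24.1% fit the same denominators (3/30 and 7/29).

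- Overall attempt rate: 13/59 = 22.0%. Both family rates lie below this, so they cannot be a split of the whole sample.
- With 4 events in 30, only 1/9 = 11.1% and 3/21 = 14.3% fit, and (1 + 3)/(9 + 21) = 13.3%, the ASAP-arm rate.

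The pilot contrast is thus consistent with families who took part versus those who did not inside the treated arm, on 4 events (HR 0.72, CI 0.07 to 6.88). It has no TAU counterpart and cannot inform an interaction. The counts are inferred from the percentages.

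**3. Simulation with no true effect modification.** 102 versus 102 participants, 10,000 replicates, two-sided 0.05.

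- Outcome: Y = −0.40·T − 0.5·U + √0.75·e, where T is arm, U is favourable prognosis, and U and e are standard normal.
- Engagement M: logit P(M = 1) = −0.85 + 1.7·T, plus 0.8·U in both arms (equal selection) or s·T·U with s = 0.8 or 1.6 (treated arm only).
- Baseline moderator: logit P(M = 1) = 0.8·U, the same in both arms.
- Test: the T×M term in a linear model.

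Only the 204 and the 0.05 come from the plan; the rest is assumed.

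| Scenario | Engaged, control / treated | False interaction | Effect, non-engaged / engaged (SD) |
|---|---|---|---|
| Baseline moderator | 50% / 50% | 5.1% | −0.40 / −0.40 |
| Treatment shifts engagement, no selection | 30% / 70% | 4.7% | −0.40 / −0.40 |
| Equal selection in both arms | 32% / 68% | 4.6% | −0.27 / −0.28 |
| Selection in treated arm only, s = 0.8 | 30% / 68% | 22.1% | −0.16 / −0.52 |
| Selection in treated arm only, s = 1.6 | 30% / 64% | 46.9% | −0.04 / −0.60 |
| As above, treatment effect zero | 30% / 64% | 46.6% | +0.36 / −0.20 |

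The mechanism can be checked by hand. With selection in the treated arm only, the interaction equals −0.5 times the prognosis gap between engaged and non-engaged treated participants: −0.364 / −0.5 = 0.73 SD for s = 0.8, and −0.556 / −0.5 = 1.11 SD for s = 1.6. The average effect is intact: 0.68 × (−0.52) + 0.32 × (−0.16) = −0.40. Only the split is an artefact.

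**4. Follow-up symptom scores (secondary).** Let M be a follow-up score that treatment lowers by 0.4 and whose link to underlying severity treatment weakens by a fraction k. The false-interaction rate is 5.0%, 5.6%, 11.1% and 53.3% for k = 0, 0.5, 0.8 and 1. The inflation is small unless treatment removes nearly all of the link.

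**The case against.** The strongest reply has four parts.

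- **The analysis is exploratory and H1 does not depend on it.** True, and it limits the consequence. But H2 states engagement as a hypothesis, and an exploratory label answers concerns about power and multiplicity, not about selection.
- **Engagement could be defined in every arm.** TAU staff work with families and BRITE alone has a family component, so a reader who infers that the interaction cannot be tested at all goes too far. What stands is that no common definition or instrument is given, and that a defined version would still be a post-randomisation, self-selected variable.
- **The Assessments wording is tentative.** A reader might infer that the plan uses follow-up symptom scores as moderators. The documents do not support that: the sentence explains why scales are repeated, H2 does not name these scales, and no planned analysis conditions on a follow-up value. The remaining point is only that the plan does not say the baseline value is meant.
- **The pilot text does not call its family result moderation.** Correct. It is background and not an error in the plan; it shows only that the available precedent is a comparison inside one arm.

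It could also be argued that the cited moderator methods already imply baseline variables. The plan does not say so, and its own named moderator would then breach the rule.

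**Conclusion.** The point holds for family engagement. As written, H2 would test a post-randomisation, partly arm-delivered and undefined variable as a moderator, and a positive result could not be told apart from differing selection into engagement. The size is conditional: 22% to 47% false interactions instead of 5%, if engagement depends on prognosis in the treated arm only, at log odds ratios of 0.8 to 1.6 per SD, with a prognosis-outcome correlation of 0.5. The documents give none of these strengths.

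A reader might infer that any effect of treatment on engagement creates false moderation. The check does not support this: a shift alone left the test at 4.7%, and equal selection left it at 4.6%, though the latter biased the effect within both strata. Prior attempt as a moderator is not in question, and H1 is untouched. The wording on symptom measures is a minor clarification.

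**What to change.** State one rule in the Specific Aims (H2), Assessments, Outcome measures and Primary aims (H2) text: moderators, including any that enter the combined profile, are values recorded before randomisation.

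- Eligible variables already in hand are prior attempt; baseline FACES-IV, MSPSS, PHQ-9, SCARED, CRAFFT and PSQI; and the two-item baseline trauma measure. The Outcome measures text names the CTQ, which is not in Table 1, so that text should be aligned with the table.
- Remove family engagement from H2's moderator claim. Define it, and report it by arm as a descriptive process measure labelled non-randomised.
- Keep baseline FACES-IV as the family-climate moderator already listed. It measures a different construct and does not test engagement.

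The cost is wording plus one real loss: a stated Specific Aims hypothesis, engagement as a moderator, is given up. No new data are needed for the moderator rule; describing engagement requires a simple attendance record if none is kept.

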### **III. RESEARCH METHODS**

#### **Overview of Study Design.**

##### Participants

Participants will include adolescents 12-17.11 years of age (N=250) who either 1) present to the inpatient psychiatry unit with recent suicidal ideation with plan or intent and/or a recent suicide attempt, or 2) are hospitalized on a medical floor for a suicide attempt. Participants must be English speaking because the treatment is not validated in any language other than English. Additionally, adolescents must own a smartphone, tablet, or device on which the Brite app can be utilized. Exclusion criteria include current (i.e., within the past two weeks) psychosis, mania, <85% of ideal body weight, and any cognitive disabilities necessitating additional testing (e.g., IQ <70, recent concussions with ongoing symptoms, etc.), as these conditions may require more intensive interventions or limit comprehension of the intervention components. Additionally, we will exclude participants being discharged to a residential treatment facility due to the level of supervision by professional adults in those facilities. The idea of the study is that the youth will return to his/her environment and will have the ability/need to use her/her safety plan while facing her/her real life problems. Residential treatment is very similar to the inpatient setting in that it is very treatment oriented and there are numerous restrictions about electronics. Lastly, youth who does not have a responsible adult who has the ability/authority to consent for research participation (e.g., youth in the custody of child protective services) will be excluded. We will oversample males and ethnic minorities so that each group constitutes at least 25% and 35% of the total sample, respectively.

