***Client Satisfaction.*** Client satisfaction will be obtained from the patient and caretaking parent using an adaptation of the Computer System Usability Questionnaire (CSUQ) to assess satisfaction with the phone app. The PSSUQ will be filled out by the participant, and is based on earlier measures designed to predict the adoption of technology, based on two main factors: ease of use (easy to learn, access, flexibility, quality of sound, quality of visual display) and usefulness (able to access when needed, helpful when used), which are scored along a 7-point Likert Scales with good psychometric properties (Davis, 1989; Lucas & Spitler, 1999). Exit interviews will also take place to measure satisfaction. Participants who are randomly selected to complete an Exit interview assessment will be given an additional \$25 payment. Participants will only be paid after completion of the assessment.

**Treatment Utilization.** Treatment history will be obtained at baseline, including services received for psychiatric complaints and medications taken. History will also be obtained at baseline and recent use during all follow-up assessment calls using the Child and Adolescent Services Assessment [CASA] (Ascher & Farmer, 1996).

**Suicide Free Days.** The adolescent version of the Longitudinal Interval Follow-Up Evaluation (A-LIFE): Psychiatric Status Ratings (PSR) score sheet (Keller et al., 1987) will be used to evaluate suicide free days. This measure is used to record symptom variations that have occurred since the last assessment. The extent of the subject's recovery from previous episodes of DSM-IV disorders as well as the occurrence and degree of severity of any new disorders is recorded using a 4-point rating over monthly intervals on the PSR score sheet.

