H3: Cost per outcome achieved will be lower for each of the interventions (ASAP + BRITE + TAU; ASAP alone; BRITE alone) compared to TAU at Week 24 Weeks follow-up. Cost per outcome achieved will be most advantageous for ASAP + BRITE + TAU. We will adopt a societal perspective on costs, assessing the cost of all usual health services, costs of services in other sectors (e.g., school),

and costs to the families (e.g., out-of-pocket costs, missed time from work). This perspective will provide the type of data relevant to health care managers and health policy makers who would make decisions about whether or not to adopt these interventions. We will conduct a series of incremental cost-effectiveness analyses (CEA) comparing ASAP + BRITE + TAU, ASAP, BRITE, and TAU.

**Cost effectiveness ratio (CE ratio).** Below, we provide a sample computation of a CE ratio, comparing ASAP to TAU and using change in *quality-adjusted life years (QALYs)* as the clinical outcome metric.

*Incremental Cost-Effectiveness =*

$$\frac{(\text{Direct ASAP Intervention Costs}) + (\text{Total Service \& Family Cost}_{\text{ASAP}} - \text{Total Service \& Family Costs}_{\text{TAU}})}{[\Delta \text{Mean QALY}_{\text{ASAP}} - \Delta \text{Mean QALY}_{\text{TAU}}]}$$

Experts have noted that there are numerous empirical challenges to accurately estimating incremental cost-effectiveness ratios (Gold et al., 1996). We next describe our procedures for assessing each component of the CE ratio, namely, the CE clinical metric and the costs of the ASAP and BRITE interventions, other services and family costs.

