**Clinical metrics.** We will conduct cost-effectiveness analyses using several clinical metrics that may be useful to decision-makers. First, we will calculate CE ratios using QALYs, this is the recommended metric by experts (Gold, Siegel, Russell, & Weinstein, 1996). Specifically, we will calculate QALYs using the PEDSQL (Varni, Seid, & Rode, 1999). However, this may not be the most meaningful outcome to clinical decision-makers. For this reason, we will also calculate CE ratios using an additional clinical metric, number of days free from suicide attempt and/or ideation (SFD). We will follow methods used in studies of the cost-effectiveness of depression treatment (Lave, Frank, Schulberg, & Kamlet, 1998; Lynch et al., 2017; Lynch, Dickerson, Clarke, et al., 2011). We will calculate SFDs using data from our suicide attempt and ideation outcome measures. Total SFDs will be calculated by summing estimated daily SFD values over the 6-month study period.

**Overall approach to measurement of cost.** In our analysis, costs will be assessed with the following general strategy: (a) calculate direct costs of ASAP and BRITE, including intervention (labor, equipment, supplies, facilities, management); (b) calculate total other service use and expense for each participant, in each arm of the study (ASAP, BRITE, ASAP+BRITE+TAU, TAU) using the CASA; and (c) family costs (out-of-pocket expenses, parent missed time from work). Note that this approach includes all services as “costs” for youths in each arm, not simply the cost of the new intervention programs. This methodology will allow us to capture any cost-offset of participation in the ASAP, BRITE, or ASAP + BRITE + TAU programs or, conversely, any increase in costs associated with additional service utilization by youths in these arms. This same strategy will be used for determining costs of the TAU arm (counting all service utilization as a cost associated TAU).

**Measurement of direct intervention costs.** An intervention “input” will be defined as any service provided to the intervention groups that is not provided to the TAU control group by the research team. We will not include research-specific inputs on either side of this calculation, such as time spent conducting baseline assessments. The direct costs of the intervention programs are the salary and fringe benefits for labor inputs (e.g., therapists, appointments clerks); costs of medical office space to

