conduct the intervention meetings; costs of treatment manuals and materials and therapy supplies; and general administration and overhead. Purchased inputs (e.g., manual printing) will be valued at their invoiced cost. Professional labor inputs will be valued using unit cost estimates developed from a national database (see costing algorithm).

**Measurement of utilization of services (Total Service Costs).** Comprehensive service use profiles will be developed on every participant. We will obtain data on utilization with the CASA, Child Health Services Screen. The CASA collects comprehensive data on all types of health services received by the participant in any health care setting, associated with treatment for the target conditions of the study (i.e., internalizing symptoms). We will also collect family out-of-pocket expenses from the CASA. Parent time missed from work will be assessed using the Family Economic Impact Interview, Employment module (FEII-E) (Lynch & Dickerson, 2012).

**Costing algorithm.** To assign costs to the utilization data and the mental health professional services used in the interventions, we will develop a set of unit cost coefficients using the Medical Expenditure Panel Study (MEPS), a nationally representative survey of health care utilization and cost that includes comprehensive assessment of health care services including mental health services (Agency for Healthcare Research and Quality, 2004). Similar approaches have been used by other investigators conducting CEA of mental health interventions (Schoenbaum et al., 2001). Health care costs will be converted to constant dollars by using the cost conversion coefficients for a year in the middle of the study period. This approach eliminates the effects of inflation on expenses and removes the burden of adjusting for inflation from the cost and cost-effectiveness models.

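### The costed services are defined by internalizing symptoms, so medical care of a suicide attempt can fall outside a cost analysis promised as societal

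*Combined protocol and SAP*

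**What the plan says.** The costing plan is set out under H3 in the Statistical analysis section of the combined protocol and SAP.

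- **Perspective (H3 paragraph).** "We will adopt a societal perspective on costs, assessing the cost of all usual health services", together with services in other sectors and costs to families.
- **Overall approach to measurement of cost.** Step (b) is to "calculate total other service use and expense for each participant", in every arm, with the CASA as the source. The TAU arm is handled the same way, "counting all service utilization as a cost associated TAU". The purpose is explicit: "This methodology will allow us to capture any cost-offset of participation".
- **Measurement of utilization of services (Total Service Costs).** The CASA is said to cover "all types of health services received by the participant in any health care setting", but the same sentence goes on to restrict these to services "associated with treatment for the target conditions of the study (i.e., internalizing symptoms".
- **Treatment Utilization (Outcome measures).** The baseline wording is also tied to condition: "Treatment history will be obtained at baseline, including services received for psychiatric complaints and medications taken".

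No claims data, medical records or other source of health service use is planned. The Family Economic Impact Interview covers parents' missed work only.

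**The concern.** The restriction is by reason for treatment, and the reason given is not what this trial treats. The aims and outcomes concern suicidal ideation, non-suicidal self-injury, suicide attempts and re-hospitalization. Treating an overdose or a wound is not, in ordinary usage, treatment of internalizing symptoms.

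That care matters to this analysis. The Background lists the medical care of young people who attempt suicide among the short-term costs of the problem. The Impact paragraph expects savings to health systems and families from less suicidal behavior and fewer rehospitalizations. The Participants section admits adolescents who "are hospitalized on a medical floor for a suicide attempt", so non-psychiatric hospital care of an attempt is a recognised event in this population.

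An analyst who followed the service-use definition to the letter would produce a cost numerator narrower than the perspective stated for H3. A second analyst who followed the overall-approach paragraph would produce a different total from the same participants.

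**Working it through.** **1. The sections side by side.**

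| Section | Scope of services counted |
|---|---|
| H3 paragraph | All usual health services, other sectors, family costs |
| Overall approach to measurement of cost | All services in each arm, taken from the CASA; any offset captured |
| Measurement of utilization of services | Health services in any setting, if tied to the study's target conditions, glossed as internalizing symptoms |

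The first two rows are unrestricted. The third, the only one that defines the content of the data used for costing, is restricted.

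**2. Which care is at risk.** The limit is by reason and not by setting. Psychiatric readmission and outpatient mental health care would probably be classed as care for internalizing symptoms and counted. Emergency care could be counted or not, depending on how it is classed. The care most exposed is medical treatment of the injury or overdose itself.

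**3. Direction.** The plan's sample ratio has as its numerator the direct intervention cost plus (service and family cost in the intervention arm minus the same in TAU). Let

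- pT and pA be the proportions attempting in the TAU and intervention arms,
- C the acute-care cost per attempter, and
- s the share of C that is not recorded as care for internalizing symptoms, with s and C taken as equal in the two arms.

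The costs left out are s × C × pA in the intervention arm and s × C × pT in TAU. The numerator is therefore too high by s × C × (pT − pA). With a positive QALY difference, this makes the ratio less favorable to the intervention whenever pT exceeds pA.

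**4. Size.** The plan states no service cost, cost per attempt or cost-effectiveness figure, so there is none to reproduce. The available inputs are the pilot attempt rates (Preliminary Data: 31.0% in TAU, 13.3% with ASAP + BRITE + TAU, p=.10) and 51 retained participants per cell (Power Analyses).

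- Difference in proportions: 0.310 − 0.133 = 0.177.
- Attempters per cell: 51 × 0.310 = 15.8 and 51 × 0.133 = 6.8, a difference of about 9.0.
- Missing offset per participant: 0.177 × s × C.

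| s (assumed) | Missing offset per participant |
|---|---|
| 0 | 0 |
| 0.25 | 0.044 C |
| 0.5 | 0.0885 C |
| 1 | 0.177 C |

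The documents give neither s nor C.

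**The case against.** The strongest reply is that this is loose wording and not an exclusion. The governing term is the study's target conditions, with internalizing symptoms only as a gloss. If the target is suicidal behavior, care of an attempt fits the governing term. The overall-approach paragraph says more than once that all services count, and the service-use section itself opens by promising comprehensive profiles. No sentence excludes emergency, medical-floor or injury care. How CASA interviewers classify such care cannot be seen from the documents.

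Most of this stands. A reader might infer that the plan leaves out emergency and hospital care altogether. The documents do not support that, because the limit is not by setting and the stated intent is broad. A reader might also put a dollar value on the gap and conclude that the cost difference could change sign. That is not supported either: s, C and the cost of the interventions are all absent. The pilot difference has p=.10 and compares only the combined arm with TAU, so it says nothing about ASAP alone or BRITE alone. The direction of bias is itself conditional on fewer attempts in the intervention arms.

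What does not stand is the suggestion that nothing needs changing. The gloss is introduced as a definition, it is wrong for this trial, and it sits in the sentence that defines the only service-use data. The sensitivity analyses and bootstrapping under Model fitting deal with uncertainty in parameters; they do not restore services that were never counted.

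**Conclusion.** The point holds as an unreconciled conflict of scope. The plan promises all services, while its operational definition, read literally, can leave out medical treatment of an overdose or injury from an attempt or self-injury. If the interventions reduce attempts, the effect is to understate the cost-offset and bias the incremental ratio against them. At pilot rates for the combined arm the understatement runs from 0 to 0.177 C per participant as s goes from 0 to 1, assuming equal s and C in the two arms.

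The consequence is confined to H3, the cost-effectiveness aim. The efficacy analyses are untouched. The wording should still be corrected, because following it literally would answer H3 from a narrower perspective than the one stated.

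**What to change.** In the section on measuring utilization of services, replace the parenthetical gloss on internalizing symptoms with a scope that matches the H3 and overall-approach paragraphs. Suggested content: the costed services are all those promised under the societal perspective, expressly including emergency, medical-floor, injury and psychiatric care for suicidal ideation, self-injury and suicide attempts, with one rule applied identically in all four arms. Keep an internalizing-only costing as a sensitivity analysis, so that the effect of the scope can be seen.

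Confirm how the CASA has been administered. If interviewers have recorded services whatever the reason for treatment, the change is one of wording and coding, using the same interview and the planned Medical Expenditure Panel unit costs. If they applied the narrow definition, it is a data-collection matter, and services not asked about may not be recoverable. Recruitment is scheduled from September 2018 to December 2021 and the document's approval date is 10-01-21, so many interviews may already be complete.

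The price is more service coding and more variable cost totals, since acute medical care is infrequent and may be expensive when it occurs.
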